To preserve the controlled nature of this experiment, each subject will work with three experimenters. After completion of screening and enrollment, the subject will be assigned to either the active or control group by the Clinical Monitor (CM). The CM will use the randomization list provided by the Biostatistics group and the UW Institute for Clinical and Translational Research (ICTR) for this study, and will issue the appropriate device (Control or Active). The CM is the only person in the study who will know which group to which each subject is assigned. The PI will then instruct each subject in the features and use of the PoNS and follow a standardized stimulus intensity level setting procedure with the subject. The second investigator, specifically the Study Coordinator, will conduct and oversee all testing. A third investigator (Physical Therapist) will perform the actual intervention. Subjects will be instructed that they must not tell the therapist what they feel on their tongue, or ask questions about the stimulation since the PT will not be able to answer these questions. If the subject has questions or feels the need to report anything about the device or stimulation, they are to address these only to the PI, in confidence. This will prevent treatment and testing bias by ensuring that the therapists and Study Coordinator are blinded to the subjects' treatment group identity.

To help preserve the controlled nature of this experiment, subjects will also be instructed that they must not discuss the stimulation, the group they think they are in, or discuss details of the intervention with any other participants in the study or with family members. They may interact with other participants as long as their discussions are not related to the study. Subjects will be discouraged from congregating or socializing outside of the study in order to maintain blinding.

Lab study visits will take place at the Tactile Communication Neurorehabilitation Lab (TCNL) at [name]. Study duration is expected to be 3 years, from time of IRB approval to the completion of data analysis.

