In stage 1, subjects will complete the twice-daily training sessions in the lab under the supervision of a Physical Therapist. In stage 2, subjects will complete the twice-daily training sessions at home for 6 days per week. They will return to the lab once each week for a training session to correct and progress their program. Every three weeks they will be re-tested on the primary and two secondary metrics. In stage 3, subjects will no longer use the PoNS device. They will return to the lab for testing every three weeks.

Table 4, below, represents the approximate timeline of events that will occur for each subject

during the study. A typical daily training schedule for the 14-week period of the study for each subject is shown in Table 5. Details of how subjects will be trained and the progression of the exercises are discussed in each subsection.

A Remote Audio Visual (RAV) training session may be performed in place of the in-lab weekly training session for weeks 3, 4, 6, 7, 9, 10, 12 & 13 in the event that the subject does not live locally, defined as a distance greater than a 4-hour drive from the lab, or for any instances, made on a case-by-case basis by the PI, when extenuating circumstances prevent a subject from attending an in-lab training session. In order for this to occur, subjects are required to have computerized video communication capability (e.g., Skype, FaceTime), and 2 assistants (one for safety and one to handle the video interface).

Table 4 – Event timeline for each subject in the study

	Initial Visit	Stage 1 (2 weeks)		Stage 2 (12 weeks)			Stage 3 (12 weeks)
		In lab 2x/day	Last P.M. of 2nd week	At home 2x/day	In lab 1x/day per week	Every 3- weeks	Every 3 weeks
Screening, Health History	X						
Demographics	X						
Informed Consent	X						
Randomization	X						
Testing	X		X			X	X
CN-NINM Training		X		X	X		
Adverse events		X	X	X	X	X	X

Table 5 - Daily Training Program

Morning:	Movement Training (warm up)	10 minutes
	Balance Training with PoNS	20 minutes
	Gait Training with PoNS	20 minutes
	BAT with PoNS	20 minutes
	- 3 to 4 Hour Break -	
Afternoon:	Balance Training with PoNS™	20 minutes
	Movement Control Training	20 minutes
	Gait Training with PoNS™	20 minutes
Evening:	BAT with PoNS	20 minutes

Movement Training (warm up)

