Data Access and Management

The TCNL will work with ICTR to develop a database in OnCore[®] that will capture test scores (both written and electronic), and associate the unique identifier to the file for each subject. The PI, Study Coordinator, Clinical Monitor, PTs and designated study staff will have access to the database during the course of the study. It will be the responsibility of the PI to ensure data are entered into the OnCore database in a timely and consistent manner. Data are recorded on data collection forms, transcribed onto case report forms (CRFs) and entered into the OnCore database by study staff. An independent staff member reviews the data collection forms, CRFs and verifies that data were entered correctly. Treatment group and personal identifying information will not be entered into the OnCore. These records will be maintained in a separate secure file location to maintain control of the study and avoid potential experimenter bias.

Data captured on all source documents from the study (demographics, Health Questionnaire, CRF's, ADE's, SAE's, assessments) will be entered into an OnCore database managed by the Data Monitoring Committee (DMC) of the Institute for Clinical and Translational Research (ICTR), an NIH-funded program comprising UW faculty not associated with the funding source or TCNL and knowledgeable in the Neurorehabilitation field. A US Army Medical Department Medical Research and Materiel Command (USAMRMC) Monitor has been assigned to protocol 2014-0002 and will perform site visits and review study data. The USAMRMC Monitor will compare data on data collection forms and case report forms (CRFs) with data entered in OnCore, including but not limited to accrual, study data, adverse events, serious adverse events and protocol deviations. Any discrepancies will be issued and resolved using the querying functionality in OnCore. Results of the monitoring performed by the USAMRMC Monitor are available for DMC review.

Additionally, the study will be monitored annually by the DMC. The DMC members will review protocol-specific reports created by statisticians using data pulled from the ICTR OnCore clinical

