1. PoNS Stimulation. The experimental apparatus cannot deliver a dangerous level of electric current. Furthermore, subjects will pre-set the intensity level to within the preferred stimulus intensity range, between sensation threshold and maximum level without discomfort. Subjects can remove it from their mouth if it does not feel comfortable.

Although no data are available on the effects of long-term electrotactile stimulation in the mouth, we have never observed, nor had report of any tissue irritation following tongue stimulation on over 300 subjects and conducted under UW-Madison HS-IRB Protocols H2000-0119, H2000-0527, H2001-364, H2004-375, H2005-0192, H2007-0251, H2008-0057, H2010-0405, H2011-0335, and 2012-0482. We do not anticipate any problems here.

2. Excess Salivation. Salivation is a natural response to the presence of anything in the mouth. Subjects typically learn to regulate saliva by learning to swallow with the device in their mouth. This is less a risk than a side effect.
3. Disease Transmission. This risk is reduced to an extremely small level by two mechanisms. First, subjects reporting transmittable diseases, or having apparent oral lesions or inflammation will not be allowed to participate in the study. Secondly, the electrode array will also be cold sterilized according to the protocol developed & approved by UWHC Infection Control Office.
4. Falls. Subjects will be protected from falls wherever possible. During in-lab balance training the subject is surrounded on 3 sides by a custom laboratory bench designed for this purpose, while the treadmill has a handrail that surrounds the participant on 3 sides. Additionally, subjects may be required to wear a safety belt during gait tests and training to prevent falls.

For RAV training sessions, two additional assistants must be present. The first assistant protects the subject from injury during performance of the various tasks (balance, gait, exercise). The second assistant handles the computer or video interface, and directs the camera angle at different positions in order for the physical therapist (PT) to observe the training as it occurs. The training session is interactive and the PT instructs the first assistant how and when to support the subject. The interaction that occurs in the RAV session with the PT, the assistant, and the subject will minimize the risk of falls in a manner equivalent to that of an in-lab training session.

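### Device reports go only to the PI so that the therapists and Study Coordinator stay blind, yet both roles can read the adverse device effect records in OnCore during the study

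*Protocol*

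**What the plan says.** Protocol, Study Design, sets the blinding rule. Subjects are told that "they must not tell the therapist what they feel on their tongue". If they have a question or something to report about the device or stimulation, "they are to address these only to the PI, in confidence". The section gives the reason as preventing treatment and testing bias by "ensuring that the therapists and Study Coordinator are blinded". The roles are separate: the Physical Therapist delivers the training, and a second investigator, "specifically the Study Coordinator, will conduct and oversee all testing".

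Protocol, Data Access and Management, describes the database. Among the source documents listed there, "ADE's, SAE's, assessments) will be entered into an OnCore database"; SAP section 8.0 repeats this. On access, the protocol says: "The PI, Study Coordinator, Clinical Monitor, PTs and designated study staff will have access to the database during the course of the study". It describes no form-level or role-level limit. It does keep treatment group and personal identifying information out of OnCore, with the aim of avoiding experimenter bias. Each subject's file carries the unique study identifier.

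**The concern.** The blinding rule treats what a subject says about the stimulation as information that could reveal the arm. That is why it is kept from two named roles. The access rule lets the same two roles read adverse device effects while subjects are still being trained and tested. A site that follows both sections as written can respect the reporting route and still pass the content to the people it was meant to exclude.

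Two things are at stake. The therapist trains each subject and decides how the exercises progress over the 14 weeks of Stages 1 and 2, so a belief about the arm could affect encouragement and challenge. The Study Coordinator conducts the testing, which includes the Dynamic Gait Index (DGI), and Pilot Study 2 in the protocol describes that index as scored by a clinician.

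**Working it through.** The point turns on who may know what, so the check sets the provisions side by side.

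1. **Who is to be kept blind** (Protocol, Study Design): the therapists and the Study Coordinator.
2. **What is to be kept from them** (same section): anything the subject feels, asks or reports about the device or stimulation.
3. **What enters OnCore** (Protocol, Data Access and Management; SAP 8.0): ADEs and SAEs along with the other source data. Not every confidential remark to the PI becomes an ADE, and the documents do not say that it does. A report that qualifies as an ADE, however, is entered.
4. **Who can read OnCore during the study** (Protocol, Data Access and Management): the PI, Study Coordinator, Clinical Monitor, therapists and designated staff.
5. **Overlap of 1 and 4**: both protected roles are on the access list.
6. **Can a record be tied to a person?** Names are not in OnCore, but the subject number is. Under Data Collection, the collection forms carry that number, and the core research team (members not listed) holds the list linking names to numbers. It is therefore an inference, though a reasonable one, that staff who test or train a subject could recognise the number.
7. **Can the text hint at the arm?** Under Device Deployment, the Control device uses a pulse frequency of about 1/2400th of the Active one, to minimise the energy delivered. Both devices are set by the same 75%-of-range formula, and Control is meant to be felt. The sensations may differ in kind, but Control is not silent.

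How informative would one record be? With 1:1 allocation (22 per arm), let p_A and p_C be the proportions of Active and Control subjects with a given kind of recorded event. Then

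P(Active | event recorded) = p_A / (p_A + p_C).

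The documents give neither p_A nor p_C. Assume only that p_A is at least p_C and above zero. If p_A = p_C, the result is 1/2 and the record says nothing about the arm. If p_C = 0, the result is 1 and the record identifies Active. The documents do not locate the trial between these limits, and they do not give the number of records.

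8. **Which outcomes are exposed?** Pilot Study 2 describes the SOT composite, the primary outcome, as an automated measure, so a tester's belief has little room to alter the score. The DGI is a clinician's rating. Differential coaching would act through the training itself and so could reach either outcome.

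**The case against.** The strongest reply is that allocation is deliberately kept out of OnCore, that the protocol is merely silent on form-level permissions, and that the consequences are limited. Balance progression follows a flow chart, training is meant to be standardised across subjects, and the primary outcome is automated. Much of this stands. The exposure is indirect, and bias in scoring the SOT is not the main worry. But silence on permissions does not answer an explicit statement that the two blinded roles have access, and removing the treatment code does not remove the event text.

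Stronger readings are tempting, and the documents do not support them:

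- **That one event record would almost certainly identify an Active subject.** No event rates are given. Control produces a sensation too, and excess salivation, attributed to having the device in the mouth, can occur in either arm. Minimizing Risk says "no data are available on the effects of long-term electrotactile stimulation in the mouth", but the same sentence reports no observed tissue irritation in over 300 subjects.
- **That oral effects go uncollected because the therapist runs the contacts.** Table 4 also marks adverse events at the three-weekly test points, no section says who collects them, and Minimizing Risk has the PI review progress daily and weekly for 14 weeks. Table 6 includes oral health in the screening questionnaire, although it lists no oral item after screening.
- **That remote sessions make matters worse.** They "may be performed in place of the in-lab weekly training session for weeks 3, 4, 6, 7, 9, 10, 12 & 13" only for distant subjects or in extenuating circumstances, and the therapist leads the in-lab sessions under the same non-disclosure instruction.

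**Conclusion.** The conflict is real and narrow. The reporting rule in Study Design and the access rule in Data Access and Management cannot both serve the stated blinding purpose for device-related events, and they should be reconciled. This rests on the text alone.

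The size of any resulting bias cannot be computed from the documents. It depends on how many device-related events are entered, how far they differ by arm, and whether the therapists or Study Coordinator read them and link them to a subject. A reader might infer that the blind is broken or that allocation is disclosed; the documents show neither. They show an avoidable route by which blinded staff may receive hints. The route bears mainly on coaching and on DGI scoring, and less on scoring of the automated SOT. The change is worth making because the protection is cheap and the protocol already relies on this blind.

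**What to change.** Amend Protocol, Data Access and Management (and cross-refer from SAP 8.0) along these lines: *ADEs and any oral or stimulation-related event are recorded on a restricted OnCore form. The form is visible to the PI, Medical Advisor, Clinical Monitor, study monitors, Data Monitoring Committee and unmasked statistician. It is hidden from the Physical Therapists and Study Coordinator until database lock. All other adverse events, such as falls, remain visible to the study team.*

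Optionally, at test visits already scheduled, the PI can ask each subject about device effects away from the therapist and record the answer on that form.

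The cost is one restricted form with its permission setting, plus a few minutes of the PI's time per test visit if the option is taken. The small downside is that entry and checking of the form must be done by someone outside the therapy and testing team. The therapist loses nothing that the reporting rule now provides, because Study Design already withholds this information. The procedure in Minimizing Risk for stopping a session when a subject shows distress is not affected.

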An independent, optional sub-study, Characterizing Functional and Structural Brain Changes Following Cranial Nerve Noninvasive Neuromodulation (AKA MRI Sub-study), will enroll 26 subjects (13 subjects in the Active PoNS™ group; 13 subjects in the Control group) who are enrolled in the main TBI Study (see [Addendum – MRI Sub-study](#)). MRI scans will be performed at important points during the study: at the beginning and end of the 2-week in-lab CN-NINM intervention period (ITP), at the end of the 12-week home training phase (HTP) and at the end of the 12-week withdrawal phase. This will yield a total of 4 data points for each subject. The sub-study MRI scans will be performed at the Wisconsin Institutes for Medical Research (WIMR), [name].

Methods

Subject Population & Selection.

All subjects will be recruited on a voluntary basis. The study will enroll 44 adults, age 18-65, presenting with a chronic balance deficit due to mTBI. Subjects who also present with other

symptoms, such as gait disturbance, mild to moderate recurrent headaches, sleep, memory, attention, or cognitive deficits, will be considered for participation. All candidates will have had a closed-head, non-penetrating, blunt, whiplash, or explosive blast-induced brain injury. Subjects will be required to provide their most recent neuroradiologic report and evidence of having completed a prescribed therapeutic regimen for their symptoms.

Study Inclusion and Exclusion Criteria.

Inclusion Criteria:

- All candidates will have a balance disorder as a result of a traumatic brain injury (TBI).
- All candidates will have a NeuroCom[®] Sensory Organization Test (SOT) composite score at least 8 points below normal after adjustment for age and height [based on normative data].
- All candidates will be between the ages of 18 and 65 (at the time of screening).
- If female of childbearing potential, the candidate agrees to use adequate contraception throughout participation in the study (from enrollment to completion).
- All candidates must have access to a treadmill.
- All candidates will be at least 1 year post-injury.
- All candidates will have a neuroradiologic scan and report after their most recent TBI.
- All candidates will be ambulatory and able to walk independently for 20 minutes.
- All candidates, if on medications, will not have had any major changes in type or dosage within 3 months of enrollment.

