Consent Process.

Candidates who have passed the phone screening will schedule a meeting with the Study Coordinator at the TCNL. The Study Coordinator will provide informed consent for the main TBI Study, answer questions and obtain informed written consent. Candidates may ask questions before signing the informed consent form. After completion of the TBI Study consent, the Study Coordinator will also provide informed consent for the [MRI Sub-study](#) and explain that participation in the sub-study is optional. All candidates will be informed that declining

participation in the MRI Sub-study will not affect their participation in the TBI Study. The PIs for both studies will be available to answer candidates' questions. All candidates are free to decline participation in either study without question if they so choose. Subjects will be given a copy of the signed consent form(s).

Subject Screening Procedure.

Once written informed consent has been obtained, the candidate will complete the Demographic Survey, the Subject Health Questionnaire, the CLQT, the SOT, and walk on the treadmill for 20 minutes. The results will be used to determine if the subject meets the study remaining entrance criteria. For those candidates that qualify for study, the SOT performed at screening will be recorded as the subject's baseline score.

Candidates who meet all screening criteria will be enrolled in the study and assigned a unique study identifier. Candidates that fail any portion of the screening will be excused from participation. All candidates who choose to enroll in the TBI Study will also be offered the opportunity to enroll in the MRI Sub-study.

Confidentiality of Screening Materials.

For persons who do not meet the entrance criteria, all personally identifiable records used for screening will be destroyed.

Compensation for Participation.

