Also, the statistician will present these results to the sponsor of the study but in the blinded fashion by identifying the treatment groups only as Group 1 and Group 2.

- **Final Analysis:** A repeated-measures ANOVA will be performed on the data derived from the 10 outcome measures gathered for each subject. Both individual (*n*=1) and cohort data set (*n*=22) analysis will be conducted to identify both specific and generalizable effects of the intervention methods. Sub-analysis by gender and age in both treatment groups will also be performed to assess the relative response of females and males.

Evidence of efficacy will be determined by significant differences in outcome measures both within and between groups after both the two-week intensive phase and at conclusion of the 14 weeks. Changes of 8 points in the SOT are considered clinically significant.

Data logs for each individual will be entered into the OnCore Data Management System used by ICTR for independent analysis and experimental verification.

Risks/Benefits Assessment

Potential Risks

1. **Electrotactile Stimulation.** The sensation could become uncomfortable at high intensity levels, which could be distressing to the subject. Some subjects have reported a mild tingling sensation that lasts from several minutes up to an hour after the stimulus is turned off. Although this sensation may feel unusual, it is not reported to be annoying and does not interfere with normal activities.

2. Excess Salivation. Subjects may experience excess salivation due to the presence of the PoNS in the mouth.
3. Disease Transmission. Because more than one subject may use the same device, there is a potential for disease transmission.
4. Falls. Subjects will be performing balance and gait tasks that may cause them to lose their balance or fall.
5. Decreased Performance or No Improvement in Symptoms. There is a risk that when subjects stop using the device, they will not retain any improvements they may have gained while doing CN-NINM training and their function will return to its prior level. There is also the possibility that CN-NINM training will not improve their symptoms.
6. Confidentiality. There is a risk that someone who is not involved in performing or monitoring this study could view study information.

Minimizing Risk

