3.2 Randomization

Subjects will be randomly assigned to one of the two treatment groups by the Clinical Monitor as they are recruited using a rolling recruitment method. Cohort assignment will be made by serially selecting from a list of 44 randomly generated three-digit subject identification numbers, with 22 subjects in each Active and Control group, respectively.

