4.3 Primary Efficacy Endpoints

The primary efficacy endpoint is the change in the SOT score from Baseline to the Week 2 and Week 14 visits. That is, if X_1 is the endpoint then:

$$X_1 = \text{Composite SOT score at Week 2 visit} - \text{Composite SOT score at Baseline.}$$

Similarly, X_2 is:

$$X_2 = \text{Composite SOT score at Week 14 visit} - \text{Composite SOT score at Baseline.}$$

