5.2 Final Analysis

The study statistician will perform the final analysis using the primary efficacy endpoints when all 44 subjects have completed their Week 26 visit. Just like at interim analysis, mean and SD of each group will be calculated. Student's *t*-test will be used to compare the two groups and *p*-value will be reported.

Secondary analyses will consider group differences on measurements at a visit as well as change from baseline.

Descriptive statistics will be calculated for outcome and demographic variables. Mean and SD will be used for numeric variables and count (percent) will be used for categorical variables. The percentage of subjects compliant in each group will be calculated. Statistical comparisons between the groups will be made using Student's t-test for numeric data and chi-squared procedures for categorical data.

Data for comparison between the treatments are collected at baseline, week 2, week 5, week 8, week 11, week 14, week 17, week 20, week 23, and week 26 visits. Each subject has up to 10 data points collected for each of the outcome variables. Data at the end of each Stage (week 2, week 14, week 26) will be used for statistical comparison between the treatment groups. Statistical comparison between groups will be based on Student's t-test.

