8.1 Definition of Baseline and Change from Baseline

Subjects are scheduled to have one baseline/screening visit. At this visit subjects should have all baseline assessments obtained prior to being randomized. Values obtained at this visit and prior to randomization are considered baseline measurements. In the case a value is not obtained at the baseline visit, a value at a prior, post-screening visit, may be used. All baseline values must be obtained prior to randomization (i.e. a value obtained after randomization cannot be considered a baseline value).

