9.0 BASELINE MEASURES

Baseline measures will be summarized by treatment group. No statistical comparisons are planned.

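### The primary SOT comparison uses raw change from the qualifying score with no baseline covariate: a valid test, but one that gives up precision and leaves the estimate open to chance baseline imbalance

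*Protocol*

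**What the plan says.** - **Entry and baseline are the same reading.** The Protocol's inclusion criteria require an SOT "composite score at least 8 points below normal after adjustment for age and height". Subject Screening Procedure adds that, for those who qualify, "the SOT performed at screening will be recorded as the subject's baseline score". Table 6 lists SOT at screening with no separate baseline SOT. SAP 8.1 agrees: "Subjects are scheduled to have one baseline/screening visit".
- **Endpoint.** SAP 4.3: "The primary efficacy endpoint is the change in the SOT score from Baseline to the Week 2 and Week 14 visits". It is written as a simple subtraction of the composite scores.
- **Test.** SAP 5.2: "Statistical comparison between groups will be based on Student's t-test". SAP 5.1 uses the same test at the interim look, where no decision is taken. The secondary analyses in 5.2, on visit values and on change, name no covariate either.
- **Protocol, Final Analysis.** A different method: "A repeated-measures ANOVA will be performed on the data derived from the 10 outcome measures gathered for each subject". No baseline covariate is named. Evidence of efficacy is to be sought within groups as well as between them, and an 8-point SOT change is called clinically significant.
- **Allocation.** SAP 3.2 assigns subjects by "serially selecting from a list of 44 randomly generated three-digit subject identification numbers". No stratification on SOT is stated.
- **Baseline handling.** SAP 9.0, Baseline Measures: "Baseline measures will be summarized by treatment group. No statistical comparisons are planned".

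**The concern.** Unless follow-up SOT rises one-for-one with baseline SOT, change from baseline depends on where a subject started. With about 17 to 22 per arm and no stratification on SOT, the arms can start some points apart by chance. A raw change score then credits part of that gap to the device, or takes it away. The t-test does not use the one measurement that could remove this, although it is recorded for every enrolled subject.

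The stake is the estimate. The Protocol's Sample Size Estimation section says the trial is meant to supply effect sizes and variances for later studies, so an avoidable shift or an inflated SD would pass into their design.

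A second consequence concerns within-group change. Subjects enter because one SOT reading was low, and the same reading is the starting point, so some rise is expected with no treatment effect at all. The Protocol counts within-group change as evidence of efficacy.

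**Working it through.** **1. The plan's own figure.** Inputs from SAP 3.1: mean changes 26.3 and 13.2 (difference 13.1), common SD of change 13.2, two-sided 0.05, 80% power. The exact two-sample t calculation gives 80.1% power at 17 per arm and 77.5% at 16. The stated 17 reproduces. The standard error of the difference is 13.2·√(2/17) = 4.53 points.

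**2. How baseline enters.** Let follow-up = constant + b·baseline + treatment effect + error, and let D be the Active-minus-Control difference in mean baseline.

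- Difference in mean change = treatment effect − (1−b)·D + noise.
- Var(change) = Var(error) + (1−b)²·SDb².
- SD left after ANCOVA = √(13.2² − (1−b)²·SDb²), with 13.2² = 174.24.

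**3. Assumed inputs.** The documents give neither SDb (baseline SD) nor b (slope). I take SDb 8 to 12 and b 0.3 to 0.9.

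**4. Precision at 17 per arm, true difference 13.1 (one df lost to the covariate).**

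| SDb | b | Variance removed | SD left | SE | Power |
|---|---|---|---|---|---|
| planned t-test | – | – | 13.2 | 4.53 | 80.1% |
| 8 | 0.9 | 0.64 (0.4%) | 13.18 | 4.52 | 80.2% |
| 12 | 0.8 | 5.76 (3.3%) | 12.98 | 4.45 | 81.3% |
| 10 | 0.5 | 25.0 (14.3%) | 12.22 | 4.19 | 85.7% |
| 12 | 0.3 | 70.56 (40.5%) | 10.18 | 3.49 | 95.3% |

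Estimating the slope also costs a little: on average the variance is multiplied by 1 + 1/(2·17 − 4) = 1.033. With that included, the four ANCOVA powers become 78.9%, 80.1%, 84.6% and 94.7%. Break-even is a variance reduction of 1 − 1/1.033 = 3.2%, so at slopes of 0.8 to 0.9 (0.4% to 3.3% removed) there is no real gain.

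**5. Size of a chance shift.** SD of D = SDb·√(2/17) = 0.343·SDb, or 2.7 to 4.1 points for SDb 8 to 12. At SDb 10 and b 0.5:

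- a 1-SD imbalance (3.43 points) shifts the estimate by 0.5·3.43 = 1.7 points;
- the average absolute shift is 1.71·√(2/π) = 1.4 points, about 10% of 13.1;
- a 2-SD imbalance, roughly a 1-in-20 event, shifts it by 3.4 points, or 26% of 13.1.

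This is part of the planned standard error, not an addition to it: 4.53² − 1.71² = 17.6, and √17.6 = 4.19, the ANCOVA value above.

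**6. Validity under selection.** A simulation admitted subjects on the observed baseline: 17 per arm, 6,000 runs per setting, equal baseline and follow-up SDs, cut-off placed at the mean of those screened. The raw-change t-test rejected in 4.7% to 4.9% of null runs and averaged 13.05 to 13.07 for a true 13.1. Selection narrowed the baseline spread, so the gain from ANCOVA shrank: power went from 86.7% to 89.2% at correlation 0.5, and from 82.2% to 82.5% at 0.8.

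**7. Within-group change.** Under the same assumptions, an arm with no treatment effect rises on average by (1−ρ)·s·√(2/π), where ρ is the correlation and s = 13.2/√(2(1−ρ)):

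- ρ 0.5: 0.5·13.2·0.798 = 5.3 points;
- ρ 0.7: 0.3·17.04·0.798 = 4.1 points;
- ρ 0.8: 0.2·20.87·0.798 = 3.3 points.

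The simulation agreed (5.2, 4.1 and 3.3). The Protocol's threshold for a clinically significant change is 8 points.

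**The case against.** The strongest reply is that nothing here is an error. The trial was sized on the SD of change for a two-group t-test, that calculation is correct, and power is about 89.5% if all 22 per arm are evaluable. Randomisation gives both arms the same expected regression to the mean. The Protocol calls the study a first, largely descriptive step. SAP 5.2 also reports visit values, which do not depend on the baseline subtraction. All of this stands. It makes ANCOVA an efficiency gain rather than a repair.

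Two stronger readings are tempting and should be resisted. A reader might infer that using the qualifying score as baseline biases the comparison between arms or inflates the type I error. It does neither, as step 6 shows. A reader might also infer that a baseline imbalance passes in full into the treatment difference. It enters with weight 1−b, which is small when follow-up tracks baseline closely.

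It is also fair to say that the size is unknown, and that no data in the text relate SOT change to starting value. At slopes near 0.9 the adjustment could cost about a percentage point of power.

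The Protocol's repeated-measures ANOVA does not answer the point. With baseline among the ten measurements, its group-by-time contrast between baseline and a later visit is again a comparison of raw changes.

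**Conclusion.** The point holds as one of precision and of exposure to chance imbalance. The planned t-test is valid, unbiased on average and correctly powered on its own assumptions. It leaves unused a covariate that is already collected, and its estimate moves by −(1−slope)·D for a baseline difference D.

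Under assumed baseline SDs of 8 to 12 and slopes of 0.3 to 0.9, adjustment removes about 0.4% to 40% of the variance. Power at 17 per arm becomes about 80% to 95% (79% to 95% once slope estimation is counted), with 86% (85%) at SD 10 and slope 0.5. Selection at entry would pull these gains down. That the covariate is missing is certain from the text; the size of the benefit is not.

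Reuse of the qualifying score matters mainly for within-group change. There, regression to the mean of some 3 to 5 points, under the assumptions in step 7, is large against the 8-point threshold. The Protocol and the SAP also name different final analyses, so correcting only one would leave them in conflict.

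**What to change.** 1. In SAP 5.2, make the primary comparison at Weeks 2 and 14 an ANCOVA of the visit composite SOT on arm, with screening composite SOT as covariate. Report the adjusted Active-minus-Control difference with its 95% CI as the effect size for later design. Keep the unadjusted t-test of change as a sensitivity analysis.
2. Bring the Protocol's Final Analysis into line, so that both documents name the same primary method.
3. In the same Protocol section, rest conclusions about efficacy on the between-group contrast. Report within-group change descriptively, with a note that it includes regression to the mean from a qualifying score.

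The cost is wording in both documents, one residual degree of freedom and the small slope-estimation penalty shown above. No new visit, measurement or subject is needed, and the planned 44 can stand. Specifying this before the data are seen also avoids a later decision on whether to adjust once an imbalance has appeared.
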